3 MODIFICATIONS

3.1 Modifications to the Approved Clinical Study Protocol

Not Applicable.

3.2 Modifications to the Approved Statistical Analysis Plan

Not Applicable.

3.3 Modifications to the Approved Addendum

This is the 1st version of Addendum 2 to the statistical analysis plan for the final analysis. There is no change to the preceding Addendum 1 which was approved on 17DEC2018.

4 INTRODUCTION

This Addendum 2 to the statistical analysis plan (SAP) for the final analysis is based on the approved SAP (Version 1.0, approval date: 25SEP2018; Version 1.1 EUR approval date: 10DEC2018), as well as the preceding Addendum 1 (Version 1.0, approval date: 17DEC2018).

Addendum 2 documents additional statistical analyses for selected efficacy variables for the final analysis. This addendum will be finalized and approved prior to the final database lock. Any revisions to the approved addendum will be documented and approved as a new version of the addendum.

The Vertex Biometrics Department will perform the additional analyses specified in this Addendum 2 for the final analysis; SAS (Version 9.4 or higher) will be used to generate all statistical outputs (tables, figures, listings, and datasets).

5 STATISTICAL ANALYSIS

This section discusses the additional analyses planned for the final analysis.

5.1 General Considerations

No change to the general considerations specified in the SAP.

5.2 Efficacy Analysis

5.2.1 Analysis of Endpoints Based on the Number of Clinical Events

Number of Pulmonary Exacerbation (PEX) through Week 24: The analysis pre-specified in the protocol based on the negative binomial regression model will be performed first. If the negative binomial regression does not converge, the analysis will be performed using the Poisson regression with the same covariates and offset.

Note: If the number of events is less than 5 in either treatment group, neither the negative binomial regression nor the Poisson regression will be performed and analysis of event counts will be based on a Fisher's Exact test.

Analysis of the number of PEX requiring hospitalization and/or IV antibiotics therapy, the number of planned hospitalizations for CF, and the number of unplanned hospitalizations for reasons other than antibiotic therapy for sinopulmonary signs/symptoms will be performed in the same manner.

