Another key secondary endpoint is the number of PEx through Week 24. Assuming a rate of PEx for the placebo group of 0.6 over 24 weeks and a 10% dropout rate, with 180 subjects and the overdispersion parameter of 0.5 in each treatment group, the power to detect a 40% reduction in the PEx rate for TC group compared to placebo group is approximately 80%, based on a 2-sided, 2-sample negative binomial regression model test for the ratio of rates, at a significance level of 0.05.

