A key secondary endpoint is the absolute change in ppFEV₁ from baseline through Week 24. Assuming a within-group SD of 7 percentage points and a 10% dropout rate at Week 24, a sample size of 180 subjects in each treatment group will have approximately 99% power to detect a difference between the treatment groups of 5.0 percentage points for the absolute change in ppFEV₁ from baseline through Week 24, based on a 2-sided, 2-sample *t*-test at a significance level of 0.05.

A key secondary endpoint is the number of PEx through Week 24. Assuming a rate of PEx for the placebo group of 0.6 over 24 weeks and a 10% dropout rate, with 180 subjects and the overdispersion parameter of 0.5 in each treatment group, the power to detect a 40% reduction in the PEx rate for VX-445/TEZ/IVA group compared to placebo group is approximately 80%, based on a 2-sided, 2-sample negative binomial regression model test for the ratio of rates, at a significance level of 0.05.

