9.3.2.2 Analysis Method

Absolute change in ppFEV₁ through Week 24: Analysis of this variable will be based on an MMRM that is exactly the same as the primary efficacy variable. However, the Day 15 Visit will not be included in the estimation of the average treatment effect through Week 24 as the treatment effect is not expected to reach the steady state at Day 15.

Number of PEx through Week 24: Analysis of this variable will be performed using a negative binomial regression model with a fixed effect for treatment, as well as continuous baseline ppFEV₁, age at screening (<18 versus ≥18 years of age), and sex (male versus female) as covariates. The logarithm of the subject-specific PEx analysis period duration (in years) will be treated as the offset in the model.

Absolute change in SwCl from baseline through Week 24: Analysis of this PD variable will be based on an MMRM similar to the analysis of the primary efficacy variable. Data obtained from Week 4, Week 8, Week 12, and Week 24 Visits will be included in the model and all of these visits will be included in the estimation of the average treatment effect through Week 24.

Absolute change in the CFQ-R respiratory domain score from baseline through Week 24: Analysis of this domain will be based on an MMRM similar to the analysis of the primary efficacy variable. Data obtained from Week 4, Week 8, Week 12, Week 16, and Week 24 Visits will be included in the model and all of these visits will be included in the estimation of the average treatment effect through Week 24.

Absolute change in BMI from baseline at Week 24: Analysis of this variable will be based on an MMRM similar to the analysis of the primary efficacy variable. Data obtained from Day 15, Week 4, Week 8, Week 12, Week 16, and Week 24 Visits will be included in the model.

Absolute change in SwCl from baseline at Week 4: Analysis of this PD variable will be based on an MMRM similar to the analysis of the primary efficacy variable. Data obtained from Week 4, Week 8, Week 12, and Week 24 Visits will be included in the model to estimate the treatment effect at Week 4.

Absolute change in CFQ-R respiratory domain score from baseline at Week 4: Analysis of this domain will be based on an MMRM similar to the analysis of the primary efficacy variable. Data obtained from Week 4, Week 8, Week 12, Week 16 and Week 24 Visits will be included in the model to estimate the treatment effect at Week 4.

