Number of events: the number of events will be analyzed using negative binomial regression similar to the analysis of number of PEx described in Section 9.3.2.2.

Note: If the number of events is <5 in either treatment group, negative binomial regression will not be performed and analysis of event counts will be based on a Fisher's Exact test.

Duration (number of days): the annualized duration of events will be analyzed using a stratified (by ppFEV₁ at screening (<70 versus ≥70), age at screening (<18 versus ≥18 years of age), and sex (male versus female)) Wilcoxon rank-sum test to assess the difference between treatment groups.

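### Addendum 2 sends a non-converged negative binomial fit for number of PEx to plain Poisson, with no stated refit or variance correction: a minor gap that matters only if the fit fails while overdispersion is present

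*SAP*

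**What the plan says.** SAP 9.3.2.2 gives the model for number of PEx: "Analysis of this variable will be performed using a negative binomial regression model with a fixed effect for treatment", with baseline ppFEV₁, age group and sex as covariates and the log of each subject's PEx analysis period as offset. Protocol 12.3.3.1.2 gives the same model. Neither says what happens if it does not converge.

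SAP Addendum 2, Section 5.2.1, fills that gap. The protocol's analysis "based on the negative binomial regression model will be performed first". Then: "If the negative binomial regression does not converge, the analysis will be performed using the Poisson regression with the same covariates and offset". With fewer than five events in either arm, "neither the negative binomial regression nor the Poisson regression will be performed", and Fisher's exact test is used. The same order applies to the hospitalisation and IV-antibiotic sub-counts, for which SAP 9.3.4.3 had said that "the number of events will be analyzed using negative binomial regression similar to the analysis of number of PEx described in Section 9.3.2.2".

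None of these sections, nor the general considerations in SAP 9.1 that Addendum 2 leaves unchanged, mentions a refit or a scaled or robust Poisson variance. Addendum 2, Section 4, also builds on SAP Version 1.1 EUR "as well as the preceding Addendum 1 (Version 1.0, approval date: 17DEC2018"). Those two documents were not available, so the statement is limited to the supplied text.

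Protocol 12.1 and SAP 7.2 size the trial on this endpoint, assuming a placebo rate of 0.6 over 24 weeks, a 40% reduction and "the overdispersion parameter of 0.5 in each treatment group". SAP 9.3.2.3 places it second among the key secondary endpoints.

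**The concern.** The fallback drops the dispersion term that the planning assumptions say is needed. If the data are overdispersed and the negative binomial fit fails for numerical reasons, plain Poisson gives standard errors that are too small, intervals that are too narrow and a test that rejects too often. The endpoint drove the sample size, and a failure there stops every later test in the hierarchy. If the fallback were ever used, an assessor would ask whether a refit was tried and why overdispersion was ignored. A correction introduced after database lock would look data-driven.

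**Working it through.** **Inputs** (Protocol 12.1, SAP 7.2): rate 0.6 on placebo; 0.6 × 0.6 = 0.36 on active; dispersion k = 0.5; 180 per arm less 10% = 162; two-sided 0.05.

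**1. Reproduce the stated power, to confirm the meaning of 0.5.** Variance of the log rate ratio = [(1/0.6 + k) + (1/0.36 + k)]/162.
- k = 0.5: 5.444/162 = 0.0336, SE 0.1833. |ln 0.6|/SE = 0.5108/0.1833 = 2.786; power = Φ(2.786 − 1.960) = 79.6%, against the stated 80%.
- Reading 0.5 as an inverse dispersion (k = 2) gives about 61%. So variance = μ + 0.5μ².

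**2. What Poisson ignores.** Variance/mean = 1 + kμ: 1.30 at 0.6 and 1.18 at 0.36.

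**3. Size if plain Poisson is used while k = 0.5.** Large-sample formula: 2[1 − Φ(1.96/√(1 + kμ))].
- μ = 0.6: 1.96/1.140 = 1.719, size 0.086.
- μ = 0.36: 1.96/1.086 = 1.804, size 0.071.

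Simulation (200,000 two-arm trials per setting, 162 per arm, Wald test). Pearson scaling multiplies the SE by √(Pearson chi-square/df) when that ratio exceeds 1:

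| Rate, both arms | Poisson SE / true SE | Size, plain Poisson | Size, Pearson-scaled |
|---|---|---|---|
| 0.6 | 0.1443/0.1649 = 0.875 | 0.084 | 0.050 |
| 0.36 | 0.1869/0.2044 = 0.914 | 0.070 | 0.050 |

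At the planned effect (0.36 v 0.6), a 95% interval misses the true ratio 7.5% of the time with plain Poisson and 4.8% with scaling. Adding one continuous and two binary covariates (assumed effects) gives plain 0.088 and 0.072, scaled 0.053 and 0.053.

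**4. When the correction does nothing.** If the Pearson ratio is at or below 1 (0.3% of trials at 0.6, 4.2% at 0.36), scaled and plain Poisson are identical. If true dispersion is zero, plain Poisson has size 0.049 and the scaled version 0.046.

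**5. How often the fallback would be triggered.** The documents give no rate. Covariate-adjusted fits, k = 0.5, none in SAS:

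| Optimiser | Setting | Not converged |
|---|---|---|
| BFGS | 0.36 v 0.6; 0.36 v 0.36 | 1 of 1,500 in each |
| Newton | 0.6 v 0.6; 0.36 v 0.36 | 0.35%; 4.9% |
| Newton, unstabilised | 0.6 v 0.6; 0.36 v 0.6 | 1.9%; 6.7% |

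The causes differ as well. In the second row nearly all failures were at zero estimated dispersion (0.025% and 0.13% were not). In the third, most occurred with overdispersion present. Both BFGS failures converged on refit, and nearly all of the unstabilised Newton failures converged when refitted by BFGS.

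**6. Effect on the PEx test.** In the second row, 4,000 null trials at 0.6 v 0.6 gave size 0.0493 both as written and with a refit. In the third, replacing plain by scaled Poisson changed significance in 3 of 1,500 null trials: 3/1,500 = 0.002, too few to be precise. The product of failure rate and excess size there is 0.019 × (0.084 − 0.050) = 0.0006. The two figures differ about threefold, and both depend on the optimiser.

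**7. Sub-counts.** Rate and dispersion are not in the documents. At an assumed rate of 0.15 and k = 0.5, 1, 2, plain Poisson has size 0.054, 0.063, 0.080; scaled 0.046, 0.047, 0.048.

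**The case against.** The case for leaving the text alone is fair. Addendum 2 already gives an ordered rule with the negative binomial first and Fisher's exact test for sparse data. The one-step fallback matches the plan's convention for the MMRM, which moves from unstructured to compound symmetry. The wording does not forbid a second attempt before non-convergence is declared. With one optimiser, adding a refit had no measurable effect on size, and with BFGS the scaling step would never have been reached. A loosely worded refit clause would add analyst choice to a rule that now has none.

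Much of this stands. It sets the severity and shapes the fix, which must name the refit. It does not remove the point. A rule that permits a refit only by silence leaves the choice to whoever runs the analysis, and the Poisson step stays uncorrected once reached. The MMRM parallel shows consistency of style, not that the Poisson variance is right.

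A reader might infer from the figures above that the PEx test runs at 0.084, or that the trial's error control is compromised. The documents do not support that: 0.084 applies only if Poisson is used while dispersion of 0.5 is present, and the negative binomial is always tried first. The opposite inference, that the effect is certainly below some figure such as 0.001, is not supported either, because the failure rate is unknown and varied widely between optimisers.

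**Conclusion.** The point holds, as minor. In the supplied text, a non-converged fit for number of PEx leads to plain Poisson with no stated refit or variance correction. Under the plan's own dispersion of 0.5 this understates the standard error by about 12% at rate 0.6 (9% at 0.36) and raises a nominal 0.05 test to about 0.084 (0.070). With zero estimated dispersion there is nothing to correct.

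The effect on overall error is expected to be small: the fallback is a contingency, most failures converged on refit, and the test is reached only after the primary and first key secondary endpoints succeed. No numerical bound is claimed. The sub-counts are outside the hierarchy, so no confirmatory claim rests on them.

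The conclusion assumes the planning rates and dispersion, assumed covariate effects, and that SAP Version 1.1 EUR and Addendum 1 do not already hold such a rule.

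**What to change.** In Addendum 2, Section 5.2.1, replace the single step by this sequence:

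1. If the negative binomial regression does not converge, refit it with the Poisson estimates as starting values and one alternative optimiser named in the addendum.
2. If it still does not converge, use Poisson regression with the same covariates and offset, and multiply standard errors by the square root of the Pearson chi-square divided by its degrees of freedom when that ratio exceeds 1. Do not scale below 1.

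Apply the same rule to the sub-counts and keep the Fisher rule as it is. If SAP Version 1.1 EUR or Addendum 1 already contains this, a cross-reference is enough.

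The cost is a new approved addendum version, which Addendum 2, Section 4, requires for any revision, before final database lock, and a small programming change. Statistically, intervals are wider when the fallback is used with overdispersion present, and the test is slightly conservative if true dispersion is zero (0.046 against 0.049).
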